9.3 Withdrawal and Discontinuation

Any subject may voluntarily withdraw (i.e., reduce the degree of participation in the study) consent for continued participation and data collection. The reason for withdrawal will be recorded on the End of Study CRF. Assessments to be performed at the termination visit (including in cases of withdrawal or discontinuation) are described in Section 10.6 and Section 21.3.

Discontinuation (i.e., complete withdrawal from study participation) may be due to dropout (i.e., active discontinuation by subject) or loss to follow-up (i.e., discontinuation by subject without notice or action). Additionally, the investigator and sponsor have the discretion to discontinue any subject from the study if, in their judgment, continued participation would pose an unacceptable risk for the subject.

Subjects also will be withdrawn from treatment or discontinued from further study participation for the following reasons:

- The subject develops a confirmed high responder inhibitory antibody to FVIII (>5 BU by Nijmegen modification of the Bethesda assay) or a low responder inhibitory antibody (≤ 5 BU but ≥ 0.6 BU) that cannot be managed by the protocol-required prophylactic dosing.
- The subject experiences a severe anaphylactic reaction to BAX 855
- The subject requires therapy with another pegylated product (e.g., PEG-Interferon)
- The subject frequently misses administration of IP (misses more than 30% of planned prophylactic doses within any 3-month period)
- The subject is non-compliant with study procedures, in the opinion of the investigator and/or sponsor
- The subject uses his/her usual FVIII therapy following the baseline infusion
- The subject requires major emergency surgery during this study
- The subject experiences a life-threatening bleeding episode (e.g., any gastrointestinal hemorrhage or intracranial hemorrhage) requiring the use of a FVIII concentrate other than BAX 855
- The subject experiences severe trauma requiring extensive FVIII replacement therapy other than BAX 855

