The dataset to be analyzed is all subjects. For subjects who developed an inhibitor, missing observation periods will be imputed at twice the rate before the study.

The use of age and race in the imputation model will allow for subgroup analyses of the primary endpoint and ABRs.

Sensitivity analyses

Sensitivity analyses will be performed similar to the primary analysis except that the negative binomial distributions used for imputations will have an artificially increased Poisson parameter by 10%, 20%, 40% and 80%. In addition, a worst-case sensitivity analysis will be performed which imputes worst-case outcomes in all subjects with missing ABR data in the observation period.

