5.5.1 Annualized Bleeding Rate

For all subjects who prematurely discontinued from the study (i.e., before ObsDay 364), and who refuse to provide data on bleeds for the remaining time till ObsDay 364, the number of bleeds (and hence the ABR), will be imputed for the second 6-month period, using Multiple Imputation techniques as described below. The ABR for a subject is calculated as the number of bleeds divided by the observation period under consideration (expressed in years).

The number of bleeds during the missing observation period in PROPEL, will be imputed for subjects taking into account, additional post-PROPEL bleeding information that is provided for the subject. Post-PROPEL bleeding information obtained for a subject (either by the subject or from another BAX 855 study), will be treated as if observed within PROPEL before the imputation procedures.

For simplicity, the imputation process is described below for a single subject (since the imputation will be performed on a subject specific basis), focussing on the period of interest for the primary endpoint (2nd 6-month period). The imputation process is described in step-by-step manner.

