5.5.1.1 Primary Endpoint Imputation

The unobserved period (which is subject specific), is defined as the subject's missing observation period in PROPEL for which there is no post-PROPEL bleed information provided.

Step1: Fitting the model

- A subject specific Negative Binomial model will be fitted. The dependent variable (left-side of the model equation), is the number of bleeds in the subject's unobserved period after ObsDay 182, taken from all subjects in the same treatment arm (low level or high level), as the subject being imputed. The offset will be the logarithm of the duration (in days), of the unobserved period for the subject (LUP). Covariates (model variables) will be stratum category, race, age at baseline and total number of bleeds observed per subject (OB), calculated for all subjects in the same treatment group of the subject for imputation.

- It is desired to avoid using bleeds in the endmost observation period as part of the covariates since the number of bleeds observed in other subjects at that time might be very low or even zero. Therefore OB, is measured in the range from ObsDay 92 up to the minimum of:
 - Last ObsDay for subject being imputed.
 - ObsDay 329.
- The following example SAS[®] code can be utilized:

```
Proc Genmod Data = <Dataset>;  
  Class <Stratn> <Racen>;  
  Model <UB> = <Stratn> <Racen> <BAge> <OB> / Dist = Negbin  
    Offset = <LUP> Link = log;  
  ODS Output ParameterEstimates = <Outdata>  
Run ;
```

Where <Dataset> represents the input dataset containing all subjects in the same treatment arm as the subject being imputed, who have at least the same amount of ObsDays as the subject being imputed. <UB> represents the number of bleeds during the subject's unobserved period (up to the maximum of ObsDay 329), <Stratn> is the numeric stratum category, <Racen> the numeric race category, <BAge> the age at baseline, <OB> and <LUP> as defined above and <OutData> the output dataset containing the parameter estimates.

Step2: Predicting the Poisson Parameter and Imputing with it

- The subject-specific Poisson parameter will be predicted from the above model fitting results by using the predicted mean number of bleeds during the subject's unobserved period (Mu) as the prediction for the Poisson parameter.
- The number of bleeds for the subject to be imputed, will be for the "imputation period" (days), where the imputation period is defined as:

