5.8 Changes from the Planned Statistical Analysis in Protocol

The Clinical Study Protocol states that the correlations between average coagulation parameters (TGA parameters: lag time, time to peak thrombin generation, peak thrombin generation, ETP and FVIII trough levels) and ABR will be assessed/displayed by boxplots. For consistency with the presentation in the 261302 continuation study, linear regression plots with 95% CIs will be used instead.

The Clinical Study Protocol states that IR at 15-30 minutes post-infusion will be calculated based on FVIII activity at baseline and steady-state. Instead, IR at C_{max} will be determined for PK assessment visits. Incremental recovery over time at scheduled IR visits will be preseted for IR at 15-30 minutes post-infusion.

In addition to the analysis described in the protocol, a listing and corresponding summary table of IR resulting from the use of 3 000 IU vials will be presented. The table will only contain descriptive statistics of IR at 15-30 minutes post-infusion by scheduled visit.

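### The SAP's imputation steps omit the protocol's rule that missing periods of inhibitor subjects are imputed at twice their pre-study bleeding rate, and SAP 5.8 does not list the omission as a change

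*Protocol*

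**What the plan says.** Protocol 14.4.1 describes multiple imputation for subjects who stop before Day 364 and give no bleed data. It then makes one exception: "For subjects who developed an inhibitor, missing observation periods will be imputed at twice the rate before the study".

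SAP 5.5.1 sets the scope of imputation without an exception: "For all subjects who prematurely discontinued from the study (i.e., before ObsDay 364), and who refuse to provide data on bleeds". SAP 5.5.1.1 then fits a negative binomial model to same-arm subjects who have at least as many observation days. The covariates are stratum, race, baseline age and the subject's own bleed count, "measured in the range from ObsDay 92 up to the minimum of" the subject's last day or ObsDay 329. Step 2 is the same for everyone: "The subject-specific Poisson parameter will be predicted from the above model fitting results". The predicted mean serves "as the prediction for the Poisson parameter", and 1,000 draws follow.

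No step mentions inhibitors, and the pre-study rate enters only through the three-level stratum. SAP 5.5.1.2, 5.5.1.3 and 7.1.2 do not restore the rule. Elsewhere the SAP mentions inhibitors only under stopping rules, safety outcomes and immunogenicity. SAP 5.8, headed "Changes from the Planned Statistical Analysis in Protocol", covers correlation plots, incremental recovery at Cmax and a table for 3,000 IU vials. Neither it nor the revision history mentions this omission.

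**The concern.** A programmer working from the SAP would not apply a rule that the protocol sets for the primary analysis, and no one reading SAP 5.8 would learn that it had gone.

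The subjects concerned are not a random subset. Protocol 9.3 gives this as a reason for withdrawal or discontinuation: "The subject develops a confirmed high responder inhibitory antibody to FVIII". It also lists a low-responder inhibitor that the protocol's prophylactic dosing cannot manage. Such a subject can easily lack some or all of the second six months. The imputation model is fitted to subjects who stayed at least as long and has no inhibitor term, so it cannot represent lost response beyond what the subject's own bleeds since ObsDay 92 show. At stake is an imputed result that is too favourable to the arm in which the inhibitor arose. SAP 5.5.1.3 reuses the procedure, so the secondary bleed-rate analyses inherit the gap.

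**Working it through.** **Plan's own figure.** For 40% against 70% bleed-free, two-sided 5% and 80% power, the continuity-corrected formula gives 49 per arm (42 without the correction). Exact power of the continuity-corrected chi-square at 48 per arm is 80.05%. The stated 48 is reproduced, and this point does not change it.

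**Inputs.**
- At least 2 treated bleeds in the prior 12 months for entry (Protocol 6.3 and 9.1).
- Planning proportions 40% and 70% (Protocol 14.1.1).
- A 182-day second period (Protocol 14.4.1) and 58 subjects per arm (Protocol 8.1).
- No inhibitor in 234 earlier subjects (Protocol 6.5).
- Assumption: the planning proportions stand in for the SAP model's prediction, since the documents give no fitted rates.
- Assumption: pre-study ABR of 2 to 5 is used for illustration.

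**Protocol rule.** P(bleed-free) = exp(−2 × ABR × days / 365.2425), with no bleed yet observed after ObsDay 182.
- 182 days, ABR 2: mean 4 × 182 / 365.2425 = 1.993; P = 13.6%.
- 182 days, ABR 5: mean 10 × 182 / 365.2425 = 4.983; P = 0.7%.
- 91 days, ABR 2: mean 0.997; P = 36.9%.
- 91 days, ABR 5: mean 2.491; P = 8.3%.

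The ABR 2 figures are upper limits, because entry requires at least that rate. This holds whether untreated bleeds are counted or not, since adding them can only raise the rate.

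**SAP route.** A Poisson mean over 182 days that matches the planning proportion is −ln(0.40) = 0.916 or −ln(0.70) = 0.357.

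| Gap | Protocol rule, ABR 2 to 5 | SAP route, 1-3% arm | SAP route, 8-12% arm |
|---|---|---|---|
| 182 days | 13.6% to 0.7% | 40% | 70% |
| 91 days | 36.9% to 8.3% | 63% | 84% |

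With the largest sensitivity inflation (+80%), the 182-day SAP figures become exp(−1.8 × 0.916) = 19% and exp(−1.8 × 0.357) = 53%.

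**Effect of one subject on an arm of 58 (182-day gap).**
- 1-3% arm: (0.40 − 0.136) / 58 = 0.5 points, up to 0.40 / 58 = 0.7 points.
- 8-12% arm: (0.70 − 0.136) / 58 = 1.0 points, up to 0.70 / 58 = 1.2 points.

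The upper ends apply when the pre-study rate is high enough that the protocol rule gives a probability near zero.

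**How many.** The one-sided 95% upper limit from 0/234 is 1 − 0.05^(1/234) = 1.27%, and 116 × 0.0127 = 1.5 subjects. This bounds any inhibitor. Those who also leave early and provide no bleed data are fewer.

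**The case against.** The strongest objection is that the affected group may be empty. Imputation applies only when a subject discontinues and provides no further bleed data. SAP 7.1.2.1 and 7.1.2.2 seek such data from the continuation study or from the subject and treat them as observed. A low-titre inhibitor that can be managed need not end participation. Two confirmed high-responder inhibitors would halt or stop the study (Protocol 8.6). All of this stands and limits the size of the point.

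A reader might also infer that an inhibitor dropout would be imputed as an average member of the arm. The SAP does not say that. It conditions on stratum, race, age and the subject's own bleeds from ObsDay 92, so bleeding after that day can raise the predicted mean. Only for someone who leaves before ObsDay 92, when that window is empty, does the draw come close to an arm average within stratum, race and age.

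Nor do the documents support the inference that a safety failure would simply be scored bleed-free. The subject contributes 1,000 draws and so counts fractionally. A subject who has already bled after ObsDay 182 is not bleed-free under either rule.

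Finally, the protocol's worst-case sensitivity analysis would cover these subjects. SAP 7.1.2 lists it but refers to Section 5.5, which does not define it. It is in any case not the primary analysis, so it does not restore the rule.

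**Conclusion.** The omission is real. The SAP's scope covers all early discontinuers without bleed data, so its silence cannot be read as keeping the protocol's exception. Following the SAP contradicts the protocol's primary analysis without saying so. An inhibitor subject who leaves and gives no data would be imputed like any other same-arm subject with the same covariates.

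The difference is large for such a subject but small for the trial: about 0.5 to 0.7 points of one arm's proportion in the 1-3% arm, or 1.0 to 1.2 points in the 8-12% arm, for a full missing period. The expected number of such subjects is probably zero. The 40% and 70% used for the SAP route are planning assumptions, not model predictions for inhibitor subjects, and shorter gaps narrow the contrast in the high arm and at low pre-study rates. This is a minor correction, worth making because it concerns the primary analysis and costs little.

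**What to change.** Add to SAP 5.5.1.1 Step 2: for a subject with a confirmed inhibitor and an unobserved period, the Poisson mean for total bleeds is 2 × pre-study ABR × imputation days / 365.2425.

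State whether that ABR counts treated bleeds only or all bleeds. Protocol 13.6 records both but bases inclusion on treated bleeds, while the bleed definition in Protocol 11.1 does not require treatment.

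The same line cannot serve the spontaneous, traumatic and spontaneous joint models in SAP 5.5.1.3, because the documents list no matching pre-study rate. For these, state in SAP 5.8 how the protocol rule is applied or why it is not. If the sponsor prefers to drop the rule altogether, SAP 5.8 should say so and give the reason.

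The cost is one sentence and one conditional line of code for total bleeds, one definition, and a short entry in 5.8, settled before database lock. The sample size is unaffected.

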14.4.2 Secondary Outcome Measures

- Total, spontaneous, and traumatic ABR, and spontaneous AJBR

For total ABR, spontaneous ABR, traumatic ABR and spontaneous JABR, separate negative binomial models will be used for the second 6 months treatment period (Days 183 to 364) as well as for the complete 12-month treatment period (Days 1 to 364).

The negative binomial model for the bleed rate will include covariates for study arm, stratum, age, and race. The multiple imputations technique will be used for incomplete observation periods as described for the primary endpoints analysis. Subgroups for age and race will be analyzed as well.

For all other outcome measures, descriptive statistics will be presented for the 2 dosing regimens. Point estimates (means and medians) and their 95% CIs will be computed to include:

- Total weight-adjusted consumption of BAX 855 for each prophylactic regimen
- Overall hemostatic efficacy rating at 8 ± 1 h after initiation of treatment and at resolution of bleed
- Number of BAX 855 infusions needed for the treatment of bleeding episodes
- HJHS
- Physical domain and component scores of the SF-36
- Physical Activity Levels

In case of surgeries, descriptive statistics will be performed for the following secondary outcome measures:

- Intra-, post- and perioperative hemostatic efficacy in case of surgery (see Section [22.5.1](#) for details)
- Intra- and postoperative blood loss in case of surgery (see Section [22.5.2](#) for details)

PK parameters before randomization will be summarized descriptively over all subjects to include:

- $AUC_{0-\infty}$, IR at 15-30 minutes post-infusion, $T_{1/2}$, MRT, CL, C_{max} , T_{max} , and V_{ss}

PK parameters after 9 months will be summarized descriptively by prophylactic treatment regimen:

- $AUC_{0-\infty}$, IR at 15-30 minutes post-infusion, $T_{1/2}$, CL, C_{max} , and T_{max}
- IR over time will be displayed as boxplots for the 2 prophylactic regimens

Correlation of VWF:Ag and PK parameters will be assessed by boxplots and Spearman rank correlation coefficient.

Descriptive statistics will be used for the secondary safety outcome measures (see Section [8.4.2.2](#)):

- Occurrence of AEs and SAEs

- Changes in vital signs and clinical laboratory parameters (hematology, clinical chemistry, and lipids)
- Inhibitory antibodies to FVIII, and binding antibodies to FVIII, BAX 855, PEG, and CHO protein

The methods of analysis for the secondary PROs measures (see Section 8.4.2.3) are described for the following PROs:

- Physical domain and component scores of the SF-36
- Physical activity levels

Change scores from baseline to completion/follow-up will be assessed for each treatment arm and tested using the minimally important difference threshold and the Wilcoxon sign rank test. Differences in the change scores between treatment groups will be tested using the minimally importance difference threshold and the Mann-Whitney U Test.

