5. LIST OF ABBREVIATIONS

Abbreviation	Definition
ABR	annualized bleeding rate
AE	adverse event
AJBR	annualized joint bleeding rate
ALT	alanine aminotransferase (SGPT)
AST	aspartate aminotransferase (SGOT)
AUC	area under the curve
AUC(0-∞)	area under the plasma concentration curve from 0 to infinity
BAX 855	product code name for Baxalta's pegylated recombinant FVIII (rFVIII)
BU	Bethesda unit
(US) CFR	(US) Code of Federal Regulations
CHO	Chinese hamster ovary
CI	confidence interval
CL	total body clearance
Cmax	maximum plasma concentration
(e)CRF	(electronic) case report form
CTA	Clinical Trial Agreement
DI	dose intensification
DMC	data monitoring committee
EC	ethics committee
eCRF	electronic Case Report Form
ED	exposure day
EDC	Electronic Data Capture
ELISA	enzyme-linked immunoabsorbent assay
EMA	European Medicines Agency
EQ-5D	EuroQol-5 dimension
ETP	endogenous thrombin potential
FVIII	factor VIII
GCP	Good Clinical Practice
GEE	general estimating equation

Abbreviation	Definition
GLM	general linear model
h	hour(s)
HAV	hepatitis A virus
HBcAb	hepatitis B core antibody
HBsAb	hepatitis B surface antibody
HBsAg	hepatitis B surface antigen
HBV	hepatitis B virus
HCV	hepatitis C virus
HCV Ab	hepatitis C virus antibody
HDL	high density lipoprotein
HIV	human immunodeficiency virus
HJHS	hemophilia joint health score
HRQoL	health-related quality of life
IB	investigator's brochure
ICF	informed consent form
ICH	International Council for Harmonisation of Technical Requirements for Registration of Pharmaceuticals for Human Use
IgA	immunoglobulin A
IgE	immunoglobulin E
IgG	immunoglobulin G
IgM	immunoglobulin M
INR	international normalized ratio
IP	investigational product
IR	incremental recovery
ITI	immune tolerance induction
IU	international unit (s)
i.v.	intravenous(ly)
LDL	low density lipoprotein
MRI	magnetic resonance imaging
MRT	mean residence time

Abbreviation	Definition
NMC	non-medical complaint
PCR	polymerase chain reaction
PD	pharmacodynamic
pdFVIII	plasma-derived factor VIII
PEG	polyethylene glycol
PK	pharmacokinetic(s)
PP	per protocol
PRO	patient reported outcomes
PTP	previously treated patient
rFVIII	recombinant factor VIII
SAE	serious adverse event
SAER	serious adverse event report
SAS	Safety Analysis Set
SF-36	Short form-36 questionnaire
SIC	subject identification code
SUSAR	suspected unexpected serious adverse reaction
SWFI	sterile water for injection
T _{1/2}	plasma half-life
TGA	thrombin generation assay
T _{max}	time to maximum concentration in plasma

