10.5 Subject Diary and Patient Reported Outcomes

A subject diary will be provided to each subject at the Screening Visit to record the following information:

1. Infusion record for BAX 855
2. Details of bleeding episodes and response to treatment. For a detailed description of bleeding episodes into different sites see Section 23.
3. Physical activity within 8 h prior to the occurrence of a bleeding episode
4. Type and duration of physical activity with a risk category of 2.5 or higher²⁹ or contact sport with a duration of ≥ 15 minutes
5. Untoward events
6. PROs (see Section 10.5.1)

For each bleeding episode, the following information will be recorded by the subject/subject's caregiver or by authorized, qualified personnel at the study site:

- Location of bleed, e.g., joint, soft tissue, muscle, body cavity, intracranial, other
- Type of bleed, i.e., spontaneous (i.e., not related to injury/trauma), injury (definitely due to injury/trauma)
- Severity of bleed, e.g., minor, moderate, major (see Table 1)
- Date and time of onset of bleed

- Date and time of each infusion of BAX 855 required to achieve adequate hemostasis
- Date and time of resolution of bleeding episode
- Overall clinical efficacy rating according to the rating scale as described in [Table 2](#) at 8 (\pm 1) hours after initiation of treatment and at resolution of bleed
- Physical activity within 8 h prior to the occurrence of the bleeding episodes

Subjects and/or their legally authorized representatives will be trained on use of the diary. The diary will be provided in electronic or paper format and remain with the subject for the duration of the study. The investigator will review the diary for completeness and request missing information periodically and in a timely manner. Untoward events recorded in the diary will be reported as AEs according to the investigator's discretion and clinical judgment. Subject entries in the diary will serve as source records. If e-diaries are used, during study participation the investigator has access to the database holding the subject diary data. After study closure, the investigator will receive the diary records for their subjects, including audit trail records, in PDF format. The data will be transmitted to the CRF by a validated transfer.

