11.1.2 Number of BAX 855 Infusions Needed for the Treatment of Bleeding Episodes

The number of BAX 855 infusions needed for each bleeding episode depends on the severity and location of the bleed and is determined by the subject, his/her caregiver, and/or clinician treating the subject, and is based upon the subject's response to treatment, using the Efficacy Rating Scale for Treatment of Bleeding Episodes in [Table 2](#). An infusion is defined as completion of administration of the calculated dose of BAX 855. If an infusion is interrupted, e.g., due to vascular access issues, and must be re-started, it will be recorded as 1 infusion. If an infusion is terminated for any reason prior to completion of infusion and not restarted, it will be recorded as an infusion; reasons for not completing the infusion will be recorded.

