7.1.2 Bleeding Episodes

Subject listings will be presented for the following items using the analysis set indicated in brackets:

- Bleeding episodes treated with BAX 855 including efficacy ratings (FAS).
- Bleeding episodes not treated with BAX 855 (FAS).
- Annualized bleeding rate and interval between bleeding episodes (SAS).
- Course of target joints (SAS).
- Magnetic resonance imaging and ultrasound (SAS).

Summary tables will be presented for the following items using the analysis set indicated in brackets:

- Descriptive statistics on annualized bleeding rate (FAS, PPAS) presented by age group, geographical location and race,.
- Comparisons presented by age group and race on:
 - Annualized bleeding rate overall and for the second 6-month study period (FAS and PPAS).
 - Sensitivity Analysis on ABR during the second 6-month study period (FAS).
- Comparisons presented by age group and race on observed annualized bleeding rate (FAS and PPAS).
- Comparisons presented by age group on:
 - Average coagulation parameters against ABR using the Spearman rank correlation coefficient, both overall and for the second 6-month study period (FAS and PPAS).
 - Reduction on ABR (FAS and PPAS).
 - Descriptive statistics on average interval between episodes [Months] (FAS and PPAS).
 - Bleeding episodes (FAS).
 - Hemostatic efficacy against number of BAX 855 infusions to treat perioperative bleeds (FAS).
- Presented by age group, bleed type, bleed severity, bleed location and bleed timing:
- Characteristics of bleeding episodes treated with BAX 855 (FAS).
- Hemostatic efficacy against number of BAX 855 infusions to treat bleeds (FAS).

Figures will be presented for the following items using the FAS:

- Dot and whisker plot (point and 95% CI) of ABR (by treatment arm).
- Multi bar plot of subject treatment profile with infusions, bleeding episodes and antibody titers.
- Linear regression plot of average observed factor VIII trough levels (IU/dL) against observed ABR.
- Linear regression plot of TGA against observed ABR.

The following information items are obtained from the eCRF:

- Bleeding episodes (Bleeding Episode eCRF panels).
- Target joints (Haemophilia A History/Blood Group/Target Joint Identification and Development of new Target Joints eCRF panels).
- Infusions to treat bleeding episodes and prophylactic infusions prior to bleeds (Study Infusion eCRF panels).
- Ultrasound (Ultrasound eCRF panel).

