where <Dataset> refers to the input dataset, <Parameter1> the first parameter to be checked for correlation, <Parameter2> the second parameter to be checked for correlation and <Outdata> the output dataset containing the inferential statistics to be presented in the summary tables. Please note that the two variables being checked for correlation must be sorted/ranked from low to high before using the SAS procedure.

Where applicable, the 95% CI on the median will be determined using the distribution-free CI for the 50th percentile from the SAS[®] UNIVARIATE procedure.

The protocol states that for subjects that leave the PROPEL study before completing the full second 6-month period (defined as ObsDay 364), subjects may provide bleeding data for the remaining days up to the end of the full 6-month period (ObsDay 364). There were two subject cases identified which fits this description in PROPEL:

- Subjects transitioning from PROPEL to the Baxalta Continuation study before ObsDay 364.
- Subjects leaving the study before ObsDay 364 but not transitioning to another Baxalta study.

The appropriate file notes have been put in place describing this process. Details of bleed information inclusion into the PROPEL analysis (primary, secondary and exploratory) is given below.

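### The 95% CIs for the two per-bleed secondary outcomes have no method for repeated bleeds in one subject; pooling bleeds would make CIs for means and proportions too narrow

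*Protocol*

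**What the plan says.** Protocol 14.4.2 introduces its list of other secondary outcomes with "Point estimates (means and medians) and their 95% CIs will be computed to include". The list includes "Overall hemostatic efficacy rating at 8 ± 1 h after initiation of treatment and at resolution of bleed" and "Number of BAX 855 infusions needed for the treatment of bleeding episodes".

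Both are recorded per bleed. Protocol 10.5 opens the diary list with "For each bleeding episode, the following information will be recorded by" the subject, caregiver or site staff, and the list includes the rating and each infusion. Protocol 11.1.2 says "The number of BAX 855 infusions needed for each bleeding episode depends on the severity and location of the bleed".

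SAP 7.2 refers both outcomes to SAP 7.1.2. That section lists the table "Hemostatic efficacy against number of BAX 855 infusions to treat bleeds (FAS") among outputs presented by age group and by bleed type, severity, location and timing. Apart from age group, these are properties of a bleed, not of a subject. On intervals, SAP 7.1.2 says only that, where applicable, "the 95% CI on the median will be determined using the distribution-free CI for the 50th percentile from the SAS" UNIVARIATE procedure. SAP 5.8, which lists departures from the protocol's analysis, does not withdraw the CIs.

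No analysis section of either document mentions correlation between bleeds of the same subject. The term "general estimating equation" stands in the protocol's abbreviation list and is used nowhere else.

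**The concern.** The subject is randomized, but the record is the bleed. Bleeds from one subject share the rater, the product, the individual PK and often the joint. Protocol 8.7.7 describes subjects with arthropathy or target joints whose recurrent bleeds take more than two infusions each, or whose ratings are usually in the lower two categories. That is a description of infusion counts and ratings clustering within subjects. A target joint is itself defined by four or more spontaneous bleeds in six months, so some subjects will contribute many records.

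The effective sample size is then smaller than the number of bleeds. An interval built from the bleed count would make the rating and the infusions per bleed in each arm look more precise than they are. These outcomes answer a named secondary objective, the hemostatic efficacy of BAX 855 in controlling bleeds.

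**Working it through.** **The plan's own figure.** The documents give no coverage figure, ICC or distribution of bleeds per subject. The nearest figure that can be checked is the sample size (40% vs 70% bleed-free, two-sided 5%, 80% power). The standard two-proportion formula gives 42 per arm, and 48.4 (49 when rounded up) with continuity correction, against 48 stated. It reproduces, and it does not depend on the present point.

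**Formulas.** Assume negative binomial bleed counts with annual mean μ and dispersion k.
- Dispersion: solve (1 + k·m)^(−1/k) = P0, where P0 is the bleed-free share and m is the mean over the period to which P0 refers.
- Design effect for a pooled bleed-level mean over 12 months: DE = 1 + (1 + k)·μ·ICC.
- Coverage of a naive 95% CI: 2Φ(1.96/√DE) − 1.

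**Inputs.**
- A: μ = 3.04 and P0 = 37.9%, from the study of children under 12 in Protocol 6.4.2. It serves only as a scenario, because this trial enrolls from age 12.
- B: P0 = 40% (Protocol 14.1.1), μ = 2.0 assumed.
- C: P0 = 70% (Protocol 14.1.1), μ = 1.2 assumed, a high-trough-like arm.

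Protocol 6.4.2 does not give the period of its bleed-free share, and the 40% and 70% feed a six-month endpoint. Each P0 is therefore read both as a 12-month share (m = μ) and as a 6-month share (m = μ/2).

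| Scenario | P0 read as | k | (1+k)·μ | DE at 0.05 | Coverage | DE at 0.20 | Coverage |
|---|---|---|---|---|---|---|---|
| A | 12 months | 2.03 | 9.21 | 1.46 | 89.5% | 2.84 | 75.5% |
| A | 6 months | 0.87 | 5.67 | 1.28 | 91.6% | 2.13 | 82.0% |
| B | 12 months | 1.53 | 5.06 | 1.25 | 92.0% | 2.01 | 83.3% |
| B | 6 months | 0.19 | 2.38 | 1.12 | 93.6% | 1.48 | 89.3% |
| C | 12 months | 5.83 | 8.19 | 1.41 | 90.1% | 2.64 | 77.2% |
| C | 6 months | 2.70 | 4.44 | 1.22 | 92.4% | 1.89 | 84.6% |

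The range is about 90-94% at ICC 0.05 and about 76-89% at ICC 0.20. At ICC 0 it is 95%.

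**Simulation.** Arms of 58 subjects, 3,000 runs, negative binomial counts with (P0, μ) = (40%, 2.0), (40%, 3.04) and (70%, 1.0), P0 read over 12 months:

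| ICC | Naive bleed-level mean | Cluster-robust, t limits |
|---|---|---|
| 0 | 95% | 94-95% |
| 0.05 | 89-92% | 93-94% |
| 0.20 | 75-84% | 92-94% |

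In the 70% bleed-free setting the robust interval covered 93% at ICC 0.05, 92% at 0.20 and 90% at 0.50.

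**Median number of infusions.** In study 261201, 95.9% of bleeds took one or two infusions, so the median is very likely one. Simulating the order-statistic CI with similar bleed distributions gave coverage of about 98-100%. It was 93-98% only when the assumed share of one-infusion bleeds was barely above half (52%). The design-effect figures do not carry over to this interval.

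**The case against.** The strongest reply is that the plan never says bleeds are independent. A reader might infer that it does from the layout by bleed characteristics, but that remains an inference. The SAP 5.9 default for qualitative variables counts subjects, and SAP 6.5 averages dose per bleed within the subject. One value per subject would remove the problem: in the simulation, the CI for a mean of subject means covered 94-96% at every ICC tried. This stands, so the finding is conditional on pooling. But SAP 6.5 also shows that the SAP spells out within-subject averaging where it wants it, and it does not do so for the rating or the infusion count. Under either reading the programmer lacks a rule.

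Second, the intervals may not be produced: the synopsis limits CIs to where feasible, and the SAP 5.9 default statistics include none. Protocol 14.4.2 nevertheless asks for them without that condition, and SAP 5.8 does not drop them.

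Third, a reader might take a coverage figure such as 76% as a property of this plan, or as a fault of the UNIVARIATE median interval. Neither is supported. The figures rest on assumed ICCs and bleed distributions, one of them pediatric. They concern means and proportions, and the median interval for infusions is conservative.

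Finally, an unused GEE entry in an abbreviation list is not evidence that an analysis was dropped.

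**Conclusion.** The point holds in conditional form. Two per-bleed outcomes are to carry 95% CIs, and no step accounts for several bleeds from one subject. If bleeds are pooled in the usual way, intervals for means and proportions are too narrow wherever the within-subject correlation is positive. The size is about 90-94% actual coverage at ICC 0.05 and about 76-89% at ICC 0.20. Both ICCs are assumptions, and so are the negative binomial counts and most of the means. With no correlation, or with one value per subject, coverage is nominal.

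The consequence is limited. The outcomes are descriptive and have no planned comparison between arms. The primary chi-square test and the negative binomial ABR models use one record per subject, so neither they nor the sample size is affected. The change is worth making because it is cheap and the outcomes serve a named secondary objective.

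**What to change.** In SAP 7.1.2, state that the bleed is the unit of summary and the subject is the cluster. Compute the 95% CIs with clustering by subject for the mean rating, the mean infusions per bleed, and any proportion of bleeds that is reported (for example excellent or good, if reported). Use either GEE with an independence working correlation and robust standard error (PROC GENMOD with REPEATED SUBJECT = subject ID), or a bootstrap that resamples subjects. Show the number of contributing subjects beside the number of bleeds. The UNIVARIATE interval for the median number of infusions can stay. Protocol Table 2 gives no scores for the four rating categories, so the coding behind any mean rating should be stated too.

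The cost is a few lines of SAP text and one REPEATED statement per outcome, with no new data. Bleed-level point estimates do not change. Intervals widen by about √DE: √1.46 = 1.21 (about 20%) and √2.84 = 1.69 (about 70%) in the most clustered scenario. With few bleeders, as expected in the high-trough arm, robust intervals still fall slightly short of 95%, so t limits based on the number of contributing subjects are advisable.
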